3.3.6.2 Missing dates of diagnosis

For missing dates of diagnosis, if the day and/or month is missing, use 01 and/or Jan. If the year is missing put the complete date to missing.

3.3.6.3 Missing death dates

If a participant is known to have died where only a partial death date is available, then the date of death will be imputed as the latest of the last date known to be alive + 1 from the database and the death date using the available information provided:

- For missing day only: Use the 1st of the month.
- For missing day and month: Use the 1st of January.

The last date known to be alive for each individual participant is defined as the latest date among all start/end/assessments/collection dates unrelated to death.

3.3.6.4 AEs with missing causality

AEs that have missing causality (after data querying) will be assumed to be related to study intervention.

3.3.7 COVID-19 Impact

Summaries of data relating to the impact of the global/country situation will be generated including the following:

- Participant disposition related to the global/country situation
- IPDs related to the global/country situation
- Listing for participants affected by the global/country situation
- Listing for participants with reported issues in the Clinical Trial Management System due to the global/country situation

3.3.8 Multiplicity/Multiple Comparisons

Not applicable.

3.3.9 Participant Disposition for Clinical Outcome Assessments

The cumulative participant disposition at each scheduled assessment where the COAs are collected will summarise the number and percentage of participants with the following:

- COAs expected
- Not expected due to disease progression
- Not expected due to death
- Not expected due to other reasons

A COA is expected as long as the participant is alive and within the first 25 cycles of treatment. Except for the palatability test where if the subject is not on treatment or if the subject transitioned to capsules the COA is not expected.

It should be noted that not all participants are expected to complete each type of questionnaire. [Table 3](#) provides an overview of expected questionnaire completions by age of participant at that assessment.

Table 3 Overview of Eligible Participants Completing Questionnaires by Respondent and Age of Participant

Assessment	Respondent	Age			
		CCI [REDACTED]	CCI [REDACTED]	CCI [REDACTED]	CCI [REDACTED]
Palatability	Parent/guardian report	Y a	Y a	Y a	Y a
CCI [REDACTED]	CCI [REDACTED]	Y	Y	Y	Y b
CCI [REDACTED]	CCI [REDACTED]				Y b
CCI [REDACTED]	CCI [REDACTED]	Y	Y	Y	Y
CCI [REDACTED]	CCI [REDACTED]	Y	Y	Y	Y
CCI [REDACTED]	CCI [REDACTED]	Y			
CCI [REDACTED]	CCI [REDACTED]		Y	Y	Y
CCI [REDACTED]	CCI [REDACTED]	Y	Y	Y	Y

^a Palatability will be assessed for participants receiving granule formulation. If the participant transitions to capsules assessment is not expected anymore.

^b CCI [REDACTED] will be completed by the CCI [REDACTED] for participants aged CCI [REDACTED] years at the time of study entry (date of signature of consent) or those who, in the opinion of the Investigator, are unable to CCI [REDACTED] CCI [REDACTED]. The CCI [REDACTED] will be used to assess CCI [REDACTED] in participants aged CCI [REDACTED] years at the time of study entry (date of signature of consent) who are able to CCI [REDACTED].

CCI [REDACTED]

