			C1 D1	C1 D15	C2 D1	C3 D1	C4 D1	C5 D1	C7 D1	C9 D1	C11 D1	C13 D1	C17 D1	C19 D1	C21 D1	C25 D1	Day 7 after transition to capsule formulation b	EoT °		
Weel	ks		1	3	5	9	13	17	25	33	41	49	65	73	81	97				
Wind	dow (days)	-28 to - 1	0	± 3	± 3	± 3	± 3	± 3	± 3	± 3	± 3	± 3	± 3	± 7	± 3	± 3	+ 4 to 14	+ 7	+ 7	

Procedure	Screen		Intervention Period in Cycles (28-day cycle) a														EoT Safety Follow-up (30 days after last dose)	Section or Appendix	
		C1 D1	C1 D15	C2 D1	C3 D1	C4 D1	C5 D1	C7 D1	C9 D1	C11 D1	C13 D1	C17 D1	C19 D1	C21 D1	C25 D1	Day 7 after transition to capsule formulation b	EoT °		
Weeks		1	3         5         9         13         17         25         33         41         49         65         73         81         97																
Window (days)	-28 to - 1	0	$\begin{array}{ c c c c c c c c c c c c c c c c c c c$											+ 7	+ 7				
Palatability (Observer Palatability) s		daily C1W 1						Twice daily C7W1											8.2.7.6
Dispense medication t		Х		Х	Х	Х	Х	Х	Х	Х	Х	Х	Х	Х	Х				6
Return medication/compliance check				Х	Х	Х	х	Х	Х	Х	Х	Х	Х	Х	Х		Х		6.2 6.4
Dispense/return ePRO device/review ePROs	Х	Х	Х	Х	Х	Х	Х	Х	Х	Х	Х	Х		Х	Х	Х	Х		6.4
Daily Drug Diary		←===						t	wice da	aily ==						→			6.4
Review Daily Drug Diary			Х	Х	Х	Х	Х	Х	Х	Х	Х	Х		Х	Х	X	Х		6.4
Blood for PD Biomarkers u		Х																	8.6.2

Procedure	Screen		Intervention Period in Cycles (28-day cycle) a Follow (30 da after 1 dose													EoT Safety Follow-up (30 days after last dose)	Section or Appendix		
		C1 D1	C1C2C3C4C5C7C9C11C13C17C19C21Day 7 after transition to capsule formulation $b$ D15D1D1D1D1D1D1D1D1D1D1D1																
Weeks		1	3	5	9	13	17	25	33	41	49	65	73	81	97				
Window (days)	-28 to - 1	0	± 3	± 3	± 3	± 3	± 3	± 3	± 3	± 3	± 3	± 3	± 7	± 3	± 3	+ 4 to 14	+ 7	+ 7	
PK blood samples v, w		Х		Х			Х				Х				х	X			8.6.1.1
Adverse Events x	X	←==															>	Х	8.4
Concomitant medication/ procedures	X	←==															===→	Х	6.5
NF1 treatments y			←===				collect	for par	rticipan	ts who	discon	tinue se	elumeti	nib prio	or to C	25 =====		=====→	

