Participants who are aged  $\geq$  5 years at the end of 25 cycles of selumetinib will be considered to have completed the study for data analysis purposes. Participants who terminate treatment prior to Cycle 25 will be followed up to collect MRIs performed as standard of care, and details of NF1-PN treatment information until the time when they would have completed 25 cycles of treatment, or they commence an alternative systemic NF1-PN treatment, whichever is the earliest. Any participant who is aged < 5 years after 25 cycles of selumetinib (or when they terminate treatment with selumetinib) will enter a safety follow-up phase until they reach the age of 5 years or commence an alternative systemic NF1-PN treatment, whichever is the earlier. Participants can continue to receive selumetinib (capsule or granule formulations) during the safety follow-up as long as they are considered to be receiving benefit in the opinion of their Investigator. The safety follow-up is designed to assess long term safety of selumetinib treatment in participants who are < 3 CONFIDENTIAL AND PROPRIETARY 40 of 168 Clinical Study Protocol -5.0 Astra Selumetinib - D1346C00004 years of age when they commence selumetinib as there are no long term safety data currently available for patients who received selumetinib at this age.

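### For outcome questionnaires other than palatability, SAP 3.3.9 still counts children who have stopped treatment as expected, so the expected counts are too high

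*SAP*

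**What the plan says.** SAP 3.3.9 defines the cumulative COA disposition table. Its general rule is "A COA is expected as long as the participant is alive and within the first 25 cycles of treatment". One exception follows: "Except for the palatability test where if the subject is not on treatment or if the subject transitioned to capsules the COA is not expected". The table has a row for COAs expected and three rows for not expected: one for death, one labelled "Not expected due to disease progression" and one labelled "Not expected due to other reasons". The section also limits expectation by age and instrument: "It should be noted that not all participants are expected to complete each type of questionnaire".

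SAP 3.3.10 lists compliance categories for the COAs. It gives an expected-count denominator for palatability only. The general rule in SAP 3.3 is that percentages use the population total unless stated otherwise.

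In the Schedule of Activities (protocol 1.3, Table 2), the row "Dispense/return ePRO device/review ePROs" is marked at visits up to Cycle 25 (except Cycle 19), at Day 7 after the switch to capsules, and at EoT. It is blank at the 30-day safety follow-up. Protocol 4.1.2 says that children who stop before Cycle 25 "will be followed up to collect MRIs performed as standard of care, and details of NF1-PN treatment information". It names no questionnaire for them. Table 3, the follow-up schedule for children under 5, shows no ePRO row among its visible rows.

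**The concern.** A count of expected forms should include only visits at which a form was due. The SAP rule ends expectation at death or at Cycle 25, with no on-treatment condition except for palatability. After a child stops, that child still adds to the expected count at each later visit, although the visible protocol plans no questionnaire there.

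The rule also conflicts with its own table. Protocol 7.1 lists disease progression as a reason to stop selumetinib, and the table has a row for children not expected for that reason. Yet a living child who stopped for progression before Cycle 25 is, by the rule, still expected. Two programmers could reasonably produce different tables from this section.

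At stake is how the COA disposition tables read, and possibly the compliance tables for five redacted instruments (SAP 4.2.10 to 4.2.14). A child with no form due could be read as a child whose form is missing.

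**Working it through.** **No stated figure to reproduce.** The documents give no expected count, completion rate or drop-out rate for the COAs. The size can be shown only over an assumed range.

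**Step 1: does the rule really omit treatment status?**
- The palatability exception removes expectation when the child is off treatment. If the general rule already required the child to be on treatment, that part of the exception would be redundant.
- The SAP amendment history shows that the exception was added on 29 April 2024 to clarify an exception, so the off-treatment condition was written for palatability alone.
- SAP 3.3.3 ends on-treatment MRI at the earliest of treatment discontinuation, data cut-off and the last day of Cycle 25. There, discontinuation and Cycle 25 are separate limits. Section 3.3.9 has only the second.

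**Step 2: are questionnaires due after stopping?** The visible Table 2 ePRO row ends at EoT, and the early-stopper follow-up in protocol 4.1.2 names only MRI and NF1-PN treatment data. Table 3 has one redacted row. SAP Table 1 places every COA row at DCO2, or at DCO1 and DCO2, and none at DCO3. The one redacted row analysed at DCO2 and DCO3 sits under safety data. This suggests, but does not prove, that the hidden Table 3 row is not a COA.

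**Step 3: size.** At a given visit, let
- s = share of living, age-eligible children off treatment (assumed);
- c = completion among those still scheduled (assumed).

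Expected-count inflation = 1/(1 − s).

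If compliance is divided by the expected count, shown completion = c(1 − s). The relative loss is s and the loss in percentage points is c × s.

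| s | Inflation 1/(1 − s) | Shown, c = 100% | Shown, c = 90% | Points lost, c = 90% |
|---|---|---|---|---|
| 10% | 1/0.90 = 1.11 | 90% | 0.90 × 0.90 = 81% | 9 |
| 20% | 1/0.80 = 1.25 | 80% | 0.90 × 0.80 = 72% | 18 |
| 30% | 1/0.70 = 1.43 | 70% | 0.90 × 0.70 = 63% | 27 |

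The inflation column needs no assumption about the compliance denominator. The completion columns do. The points lost equal s only when c = 100%.

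**Step 4: limit on precision.** The ePRO row is marked at EoT, and the SAP 3.3.4 visit windows are exhaustive. An EoT assessment could therefore fall in the window of a later scheduled visit and count as completed there. This makes c(1 − s) approximate and reduces the loss slightly.

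**The case against.** **An alternative reading of the rule.** Being within the first 25 cycles of treatment could mean still receiving treatment cycles. Where the protocol means elapsed time regardless of stopping, as in its MRI follow-up, it says so explicitly. The progression row would then have a use, and children who stopped would go there. This may be what was intended. However, it makes the off-treatment part of the palatability exception redundant, and nothing in the text says which row takes children who stopped. Palatability does need a rule of its own, because its entries are counted by days on treatment, but that does not supply the missing condition for the other COAs.

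**Redaction.** The individual COA rows of Table 2 and one row of Table 3 are hidden. The visible row concerns the ePRO device, and the survey in SAP 4.2.15 is on paper. That nothing at all is scheduled after EoT is well supported but cannot be fully verified. This limit stands.

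**Denominator.** A reader might infer that reported completion must fall by the share who stopped. The SAP does not say that compliance for these COAs is divided by the expected count. Its default is the population total, under which any understatement would come from that rule and would also include deaths. The completion effect is therefore conditional, and it is a relative loss.

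**Wider harms a reader might infer.** Three are not supported:
- The 85% alert in protocol 8.2.7.7 comes from the ePRO system's routine report and prompts contact with the family. Nothing links it to the SAP expected count.
- The MMRM in SAP 4.2.10.4 uses observed data and drops visits by the number of children with non-missing data. The expected count does not enter it.
- Reasons for stopping are not hidden, because SAP 4.1.1.1 tabulates discontinuation by reason.

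Nor is every living child counted as expected for every form: the age limits and the palatability exception already apply.

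**Conclusion.** The point holds for COAs other than palatability. Read as written, SAP 3.3.9 counts living, age-eligible children as expected through Cycle 25 after they have stopped, and for these COAs the progression row can never be filled. The expected counts are too high by about 1/(1 − s), on two conditions: the redacted COA rows follow the visible ePRO schedule, and s lies in a range that the documents do not give. A loss in shown completion follows only if compliance uses that count.

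The effect is confined to descriptive disposition and compliance tables for exploratory COAs. No primary or secondary estimate changes, and no MMRM changes. This is a minor correction worth making, with medium confidence because of the redactions.

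**What to change.** In SAP 3.3.9, define a COA as expected at a scheduled visit if the child is alive, age-eligible for the instrument, within Cycle 25, and still scheduled under the Schedule of Activities (on treatment, plus the EoT visit). Keep the palatability exception for capsule use. Place children who stopped in the progression row or the other-reasons row according to their reason for stopping.

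In SAP 3.3.10, name this expected count as the denominator of the compliance summaries for the non-palatability COAs, in place of the population-total default in SAP 3.3.

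The cost is SAP wording and table programming. No data collection changes, and SAP Table 1 schedules these COAs for DCO2.

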3.3.10 Compliance Definition for Clinical Outcome Assessments

Summary measures of compliance over time will be derived for the COAs. These will be based on the following:

- All items/questions completed
- At least meets minimum requirements for calculation of one subscale or a total score of the questionnaire (applicable to **CCI** only)
- At least meets minimum requirement for calculation of the **CCI** (applicable to **CCI**, **CCI** scale only)
- At least one question completed

For COAs with only one question (**CCI**), the category “Questionnaire completed” will be presented.

CCI compliance will be summarised for AM and PM of each visit. The participant will have complied if the **CCI** field of the diary is not missing.

The compliance for palatability will be summarised by item and week and based on the following:

- Expected number of participants
 - A participant is expected to complete Item 2 only if she/he responded ‘No’ at least once to Item 1.
 - A participant is expected to complete Item 3 only if she/he responded “No” at least once to Item 1 and or “Other” to Item 2, or having first responded “Yes” to Item 1.
- Expected number of entries
 - The expected number of diary entries for Items 1, 4, and 5 is; expected number of participants x 2 (number of daily assessments) x the number of days the participant is on treatment without transitioning to capsules in the first week of the Cycle 1 or Cycle 7 (until a maximum of 7 days).
 - The expected number of diary entries for Item 2 is: number of entries (Item 1 = “No”).

- The expected number of diary entries for Item 3 is: number of entries (Item 1 = “No” and Item 2 = “Other”) plus number of entries (Item 1 = “Yes”).
- Subjects with at least one item completed at least once (count and percentage)
 - Percentage will be calculated as the number of participants with item entry completed at least once divided by the expected number of participants in a week.
- Item completion rate (count and percentage)
 - Completion rate will be calculated as the number of actual completed item diary entries divided by the expected number of item diary entries in a cycle.

3.4 Sample Size Determination

Global Cohorts (Cohorts 1 and 2)

Approximately **CCI** participants will be dosed in Cohorts 1 and 2 to achieve **CCI** evaluable participants at the recommended granule formulation dose schema, of whom at least **CCI** participants will be aged ≥ 1 to < 4 years (with at least 3 aged < 2 years) and at least **CCI** participants will be aged ≥ 4 to < 7 years. A sample size of **CCI** participants will provide reasonable precision to characterise PK and safety.

At least **CCI** evaluable participants in each age group are required at the final recommended granule formulation dose schema.

With a minimum of **CCI** evaluable participants in each age group and **CCI** evaluable participants in total, the numbers of participants in the **CCI** age groups will fall between a combination of **CCI** to a combination of **CCI**. With sample sizes of **CCI CCI** in an age group, the power to show that the **CCI** CI of the AUC0-12 geometric mean falls within the acceptance range (**CCI** to **CCI**-fold of the SPRINT AUC0-12 geometric mean; FDA Guidance 2014) will be 90%, 99.9% and $> 99.9\%$, respectively. The power for two age groups falling within the acceptance range simultaneously will therefore be $90\% \times 99.9\% \approx 90\%$ and $99.9\% \times 99.9\% \approx 99.9\%$ for the **CCI** combination and **CCI** combination, respectively. This sample size calculation assumes that there is a **CCI** difference in exposure between the granule and capsule formulation and assumes an inter subject gCV% of **CCI** (Wang et al 2012). The choice of gCV% is based on observations from Study 89 **CCI** and the SPRINT study **CCI**).

In the dose-finding phase of this study, the exposure AUC0-12 will be monitored on an ongoing basis. The minimum sample size for each cohort and the study may be re estimated

when **CCI** evaluable participants in that cohort have provided acceptable PK exposures. The re estimation will use the observed inter-subject gCV%. [Table 4](#) below shows the minimum sample sizes required in each age group corresponding to different variability and different scenarios.

Table 4 **Sample Size Estimations based on Inter-subject gCV% and Expected Differences in AUC0-12 between SPRINKLE and SPRINT studies.**

Inter-subject gCV%	Difference in AUC0-12 between SPRINKLE and SPRINT studies		
	± 5%	± 10%	± 15%
CCI	CCI	CCI	CCI
CCI	CCI	CCI	CCI
CCI	CCI	CCI	CCI

AUC₀₋₁₂, area under the concentration-time curve from time zero to 12 hours; CV, geometric coefficient of variation.

Japan Cohort

In addition to the Global Cohorts (Cohorts 1 and 2), a separate Japan Cohort of a minimum of **■** evaluable Japanese participants aged ≥ 1 to < 7 years will be recruited in Japan.

An evaluable participant for PK and sample size calculations is defined as a participant with a PK profile on Day 1 (for an individual at least **■** samples during the 12-hour time period post first dose on Cycle 1, Day 1 and must include the **CCI** hour PK sample) without any important protocol deviations potentially impacting the PK results.

Note: “Enrolled” means a participant’s or their legally authorised representative (parent or guardian) and participant’s (if deemed appropriate as per local regulations) agreement to participate in a clinical study following completion of the informed consent process.

Potential participants who are screened for the purpose of determining eligibility for the study, but do not receive selumetinib, are considered “screen failures”, unless otherwise specified by the CSP.

4 STATISTICAL ANALYSIS

This section provides information on the definitions, derivations, and analysis/data presentation per domain.

Not all analyses will be performed for each DCO. [Table 1](#) provides detailed information on the expected outputs.

For DCO1 and DCO2, all available data will be used for the planned analyses as specified in [Table 1](#). For DCO3, the data of a subset of participants who are aged < 5 years after 25 cycles of selumetinib treatment or discontinuation of study intervention will be presented.

The starting dose schema was approved by the SRC as the recommended dose schema in both cohorts at the end of the dose-finding phase.

The analysis will be presented for the Global Cohorts (Global Cohort 1, Global Cohort 2, and both Global Cohorts combined), the Japan Cohort, and for all participants (all cohorts combined), except for the PK analyses where the Global Cohorts and the Japan Cohort will be presented separately without combining.

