a. After 25 cycles (or discontinuation of selumetinib) participants who are aged < 5 years will enter a long term safety follow-up and assessments will be performed as per Table 3. After 25 cycles of treatment if participants are > 5 years of age and unable to access commercial supply and are still receiving clinical benefit participants may be able to remain on treatment in the study. Assessments will revert to standard of care at the particular site. There will be no more data collection except SAE, overdose and pregnancy reporting. All SAEs, overdoses and pregnancies will be reported until 30 days after last dose.

b. Once participants attain a BSA between 1.10 and 1.29 m^2 they will be encouraged to completely transition to the capsule formulation, if feasible, although all participants must remain on the granule formulation until after they have completed their third cycle of treatment.

c. An EoT visit will be performed for participants who permanently discontinue study intervention for any reason (except for death, lost to follow-up, or withdrawal of consent). The EoT visit should be performed as soon as possible after the end of treatment.

d. Calculation of BSA should be done at the specified time points but since BSA determines the dose of selumetinib it should also be calculated more frequently, as appropriate, depending on the age and growth rate of the child.

e. Assessment of baseline disease characteristics includes documenting location of the target and non-target PN (if applicable), any PN-related symptoms and results of any previous genetic testing for NF1. (Participants recruited under CSP Version 1.0 will have this data entered in the EDC if available retrospectively.)

- f If clinical safety laboratory assessments, urinalysis and performance status have been done within 14 days of starting study intervention they do not need to be repeated on C1D1 if the participant's condition has not changed. If laboratory procedures were performed for alternate reasons prior to signing consent (but within the 28 day screening window), these can be used for screening purposes with consent of the legally authorised representative (parent or guardian) of the participant.

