# 8.4.1 Time Period and Frequency for Collecting AE and SAE Information

Adverse events will be collected from the time of signature of the ICF until 30 days after the last dose of selumetinib or 25 cycles of treatment, whichever is earlier. For participants taking part in the long term safety follow-up (participants < 5 years of age), after 25 cycles of treatment or end of treatment, adverse events causally related to selumetinib will be collected until they complete the study in accordance with Table 3. No AEs will be collected for participants who are > 5 years of age who remain in the study after 25 cycles of treatment.

SAEs will be collected from time of signing the ICF throughout a subject's participation in the study.

If the Investigator becomes aware of an SAE with a suspected causal relationship to the IMP that occurs after the end of the clinical study in a participant treated by him or her, the Investigator shall, without undue delay, report the SAE to the Sponsor.

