  - The PK samples will be analysed on a regular basis to inform SRC. It is expected that single and multiple dose PK from all participants dosed with selumetinib would be available within 3 months of the last participant being dosed; at this point, all participants will have palatability data available and a minimum of 3 months of safety data.
- 2 Safety and efficacy of the granule formulation:
  - A DCO (DCO2) and analysis will occur after all participants in the study (Global and Japan Cohorts) have had the opportunity to complete 25 cycles (or terminated selumetinib); this analysis will provide additional PK and safety/tolerability data, as well as palatability and efficacy data.
  - Efficacy analyses will be performed, including: ORR (assessed by ICR and investigator),
    CCI and COAs.
- 3 Long term safety follow-up for participants until they reach the age of 5 years or commence an alternative systemic NF1-PN treatment, whichever is the earlier:
  - A final analysis will occur when all participants in the study (Global and Japan Cohorts) have had the opportunity to complete their last assessment in the study, including the safety follow-up for participants aged < 5 years.

  - All of the safety/tolerability analyses will be updated with the data captured after the DCO for the analysis shown in bullet point 2 above (safety and efficacy of the granule formulation).

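### At DCO3 the SAP presents only children under 5, so SAEs arising after DCO2 in older children still on selumetinib have no planned final output, in conflict with the protocol and with other SAP sections

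*SAP*

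**What the plan says.** **Which data each cut-off uses.** SAP Section 4 says "For DCO1 and DCO2, all available data will be used for the planned analyses as specified in" Table 1. The next sentence changes the rule: "For DCO3, the data of a subset of participants who are aged < 5 years after 25 cycles of selumetinib treatment", or at discontinuation of study intervention, will be presented. DCO3 is the last planned analysis.

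**What the final analysis is meant to do.** Protocol 9.4.1, on the third analysis time point, says "All of the safety/tolerability analyses will be updated with the data captured after the DCO" that followed 25 cycles. SAP 3.1 repeats this for DCO3. Neither sentence carries an age limit. SAP 4.6 presents safety data for the safety analysis set, which SAP 3.2.3 defines as every participant given at least one dose. SAP Table 1 marks adverse events for DCO3 with no note about a subset. SAP Section 2 declares no change to the protocol's planned analyses.

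**What is still collected from older children.** Protocol Table 2, footnote a, lets children over 5 remain on study treatment after Cycle 25 if they still benefit and cannot get commercial supply. For them, "There will be no more data collection except SAE, overdose and pregnancy reporting", and "All SAEs, overdoses and pregnancies will be reported until 30 days after last dose". Protocol 8.4.1 adds "SAEs will be collected from time of signing the ICF throughout a subject's participation in the study", and Protocol 8.4.9 has all SAEs entered in the eCRF. On other events, 8.4.1 says "No AEs will be collected for participants who are > 5 years of age who remain in the study after 25 cycles of treatment".

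**How the protocol classes these children.** Protocol 4.1.2 says that those aged 5 or over at the end of 25 cycles "will be considered to have completed the study for data analysis purposes".

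**The concern.** A programmer cannot follow both SAP Section 4 and the update rule in Protocol 9.4.1 and SAP 3.1. Section 4 is the more specific statement about which data are shown at DCO3, so it is likely to be the one followed. In that case a child who was 5 or older at the end of Cycle 25 and stays on study drug is outside the DCO3 presentation. SAEs in that child after DCO2 would be in the database, with no later analysis to pick them up.

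These children would have the longest treatment of their age group in the trial. The risks the protocol monitors (cardiac, ocular, muscular and growth-plate) are ones for which a single serious event after long exposure deserves to be seen in the final report of a small, single-arm paediatric study.

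**Working it through.** The documents give no figure to reproduce here. The check is a cross-reading plus date arithmetic.

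**Inputs.** The treatment period is 25 cycles of 28 days (Protocol 1.3, SAP 1.1). Cohort 1 is aged 4 to under 7, and Cohort 2 and the Japan Cohort start from age 1 (SAP 1.1). DCO2 comes once everyone has had time to finish 25 cycles or has stopped. DCO3 comes once the under-5 follow-up is complete (SAP 3.1). Follow-up visits for children on treatment are every 6 cycles, continuing to the first visit after the fifth birthday (Protocol Table 3).

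**Step 1: length of 25 cycles.** 25 × 28 = 700 days; 700 / 365.25 = 1.92 years.

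**Step 2: who falls outside the DCO3 subset.**
- Youngest Cohort 1 completer: 4 + 1.92 = 5.92 years. Age is set at consent, which precedes the first dose, so this is a lower bound. No Cohort 1 completer is in the subset.
- Cut-off at first dose: 5 − 1.92 = 3.08 years. Completers from Cohort 2 or the Japan Cohort who start at about 3.08 years or older are also outside it.

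**Step 3: length of the DCO2-to-DCO3 window.** It depends mainly on how young the last children to finish are.
- Last to finish started at 1.0 year: 5 − 1 − 1.92 = 2.08 years to the fifth birthday. Waiting for the next 6-cycle visit adds up to 168 / 365.25 = 0.46 years, giving 2.54 years.
- Started at 2.0 years: 5 − 2 − 1.92 = 1.08 years.
- Started at 3.0 years: 5 − 3 − 1.92 = 0.08 years.

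The window is therefore roughly 0 to 2 years, or slightly more.

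**Step 4: where an SAE in an older child still on drug would appear.**

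| Time of SAE | Collected? | Analysed? |
|---|---|---|
| After that child's Cycle 25, up to DCO2 | Yes | Yes, DCO2 uses all available data |
| After DCO2, up to DCO3 | Yes, to 30 days past the last dose | Yes under Protocol 9.4.1, SAP 3.1 and SAP 4.6; no under SAP Section 4 |

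Only the second row is in dispute. The SAP's treatment-emergent window (SAP 4.6.2.1) has no age limit, so it would not remove these events.

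**The case against.** **The exclusion is intended.** This is the strongest reply. Protocol 4.1.2 treats children aged 5 or over at the end of Cycle 25 as complete for analysis, and says the follow-up exists because long-term data are lacking in children who start under 3. In both documents the update sentence sits under an item about follow-up to age 5. Footnote a speaks of reporting, which can be read as safety surveillance only. Much of this stands: it explains why visit assessments and non-serious AEs stop, and it means Section 4 is not a plain slip. It does not explain collecting on-drug SAEs in the eCRF without an analysis to receive them. Nor does it remove the conflict with the update rule and with SAP 4.6.

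**Stronger readings that the documents do not support.**
- A reader might infer that all SAEs after Cycle 25 in older children are lost. DCO2 uses all available data, so those up to DCO2 are included.
- A reader might infer that SAEs go unreported. Protocol 8.4.9 still sends every SAE to the sponsor, with onward regulatory reporting of SUSARs. What is missing is a place in the final analysis.
- A reader might infer that the long-term safety conclusion rests only on the youngest children. DCO2 gives safety over 25 cycles for every cohort.
- A reader might infer that a child is dropped on turning 5 during follow-up. The subset is fixed by age at the end of Cycle 25 or at discontinuation.
- A reader might wish to put a number on the missing SAEs. The documents give no SAE rate and no count of children likely to continue, so none can be given.

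**A table would lack a denominator.** This stands in part. Under footnote a, little or no dosing data may exist for these children, which favours a listing with a count over rates.

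**Conclusion.** The point holds as a conflict between rules with a narrow consequence. SAP Section 4 limits DCO3 to children under 5 at the end of Cycle 25 or at discontinuation. Protocol 9.4.1, SAP 3.1 and SAP 4.6 call for updated safety data without that limit. If Section 4 governs, SAEs that occur after DCO2 and before DCO3 in older children still on selumetinib reach no planned final output.

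The conclusion rests on Section 4 being read as overriding the general statements, and on at least one older child staying on study drug past DCO2. The number is unknown and could be nil, since staying requires continuing benefit and no access to commercial supply. The consequence is modest, but the text should be settled before DCO3 because no later analysis would recover the events.

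**What to change.** Reconcile SAP Section 4 and Table 1 with Protocol 9.4.1, SAP 3.1 and SAP 4.6. Add to DCO3 one listing, with a simple count of participants and events, of SAEs and deaths after DCO2 in all safety-set participants still receiving selumetinib, whatever their age. Footnote it to say that, for children over 5 after Cycle 25, only SAEs were collected for this purpose (not other AEs or visit assessments), and that exposure data may be limited. Keep the under-5 subset for every other DCO3 assessment.

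The cost is SAP wording and one output from data already in the eCRF. It needs no new data collection and no change to treatment or follow-up.
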